2. Compare the effectiveness of the two intervention sequences (1st cognitive training and 2nd mindfulness versus 1st mindfulness and 2nd cognitive training) on neurocognitive, biopsychological, biomarker, and connectome outcome variables.

METHODS

1. Study Design 3: In this single-center study (La Paz University Hospital), the pilot phase of a randomized, counterbalanced, crossover controlled clinical trial with a recycled waiting list will be conducted according to CONSORT standards. (Boutron et al., 2017).

2. Participants: A total of 40 patients (20 patients initially in the clinical trial phase and 20 on the waiting list) between the ages of 8 and 18 will be recruited from the three clinical groups in Study 1, requiring compliance with inclusion criteria (having a computer, mobile phone, or tablet with an Internet connection) and exclusion criteria (CI < 80 in Matrices). These 40 patients will be recruited from the sample participating in Study 1 using a strategic/intentional non-random sampling technique.

3. Outcome variables: In pre-/post-intervention phases, primary variables will be measured using performance tests: processing speed (SDMT); sustained visual attention (CPT-3); working memory, implicit, immediate/delayed auditory-verbal, visual-spatial, and intermodal [Clinical Memory Assessment (ECM)]; verbal fluency [Verbal Fluency Test (VFT)]; resistance to visual interference [Colors and Words Test (STROOP)]. Secondary variables in pre-/post-intervention phases are questionnaires measuring: executive functions [BRIEF-2, parent-completed version]; pain intensity and interference [BPI, self-reported by patient]; sleep quality [PROMIS and AIQ, self-reported by patient]; emotional and behavioral problems [BASC-3, parent and self-reported versions]; and mindfulness, trait level [Children and Adolescent Mindfulness Measure (CAMM)]; as well as biomarkers (inflammatory and immunological) and a neurofunctional analysis (connectome), using electroencephalogram (EEG) recordings. In the intermediate phase (3 months after the start of treatment), the BASC-3 questionnaire will be administered. Finally, at the 6-month follow-up after the end of both interventions, the BRIEF-2, BASC-3, BPI, AIQ, and PROMIS questionnaires will be included.

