
5. Statistical analyses: The statistical analyses for this third study will be described jointly for the two established objectives.

First, mixed 2x3 ANCOVAs will be used (intergroup factor, with two levels: experimental group versus control; and repeated measures factor, with three levels: pre-intervention, post-intervention, and six months), controlling for confounding variables (time elapsed since completion of the last treatment received: chemotherapy, TPH, or CAR-T). However, in the event of non-compliance with statistical assumptions such as normality, non-parametric analog models will be used. In turn, latent growth curve models will be developed.

As for the intergroup factor, Tukey's HSD parametric tests (for homoscedastic contrasts) and Games-Howell tests (for heteroscedastic contrasts) will be used to control the type I error rate per family of comparisons. Likewise, in the event of non-compliance with parametric assumptions such as normality, the Mann-Whitney U test will be used for pairwise comparisons, controlling the type I error rate with the Bonferroni correction. Regarding the intragroup factor, parametric pairwise contrasts will be performed using Tukey's WSD test (for spherical contrasts) and the

Roy-Bose test (for non-spherical contrasts); and non-parametric pairwise comparisons will be performed using the Wilcoxon test together with a Dunn-Sidak post hoc correction.

In turn, these parametric hypothesis testing procedures will be complemented with effect size indices such as omega squared, as an omnibus index, and Cohen's d, as an index for pairwise comparisons.

Conversely, where appropriate, for the intergroup factor, effect size indices for nonparametric tests such as Freeman's Theta, as an omnibus index, and Cliff's Delta, as an index for pairwise comparisons, will be used. On the other hand, for the intragroup factor, Kendall's W-type omnibus effect size indices will be applied, as well as the biserial correlation for dependent pair ranks in order to perform multiple comparisons.

Finally, for the interactive term, the effect size index f will be chosen as an omnibus test, and Cohen's d indices for simple effects.

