Finally, multiple regression analyses will be performed to predict post-treatment and 6-month follow-up measures (neurocognitive and biopsychological), coding some measures from Study 1 as predictors, such as: processing speed levels, sustained visual attention, verbal fluency, and resistance to visual interference.

6. Limitations, biases, and contingency plan: given that participant loss is expected in any clinical trial, additional participants from the previous study will be recruited in such a scenario. The multi-method evaluation approach used (objective neurocognitive tests, questionnaires, biomarkers, and connectome) will avoid the common method bias (Podsakoff et al., 2012). Anticipating the temporary limitation on pre-/post-intervention assessment tasks as a potential risk to implementation, the age-differentiated treatment editions will be implemented partially simultaneously, with a one-month delay in the start of the intervention for each age group, using that month for the pre-intervention assessment of the other group.

This project will be carried out in accordance with the ethical principles of the Fortaleza Declaration of Helsinki (2013), strictly respecting confidentiality and the requirements of Spanish/European data protection regulations, as well as the provisions of the biomedical research law (Law 14/2007, of July 3); the informed consent of patients and their legal guardians will be required.

Finally, given that the objectives of these studies have not been scientifically addressed to date in the child and adolescent population receiving CAR-T therapies, this project will make a novel, original, and relevant contribution at the scientific-clinical level, and is in line with one of the strategic lines of our institution, IdiPAZ, and its core hospital, given that it coordinates the **European Reference Network TransplantChild**.

DATA MANAGEMENT PLAN

The data management plan will include criteria for the handling and administration of scientific data following the FAIR principles (Findable, Accessible, Interoperable, and Reusable).

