INTELLECTUAL PROPERTY: The results of the project that may lead to new diagnostic techniques, modifications to existing treatments and/or protocols, medicines, medical devices, or vaccines will initially be communicated confidentially to the institution by the PI in order to determine whether they could be patentable or should be protected by intellectual property rights. The data may not be disclosed until the patents related to the research are protected, if any, or the appropriate measures are taken to protect the intangible assets.

WORK PLAN

The research team formally involved in this project consists of:

- Psychologists trained in neuropsychology to perform neurocognitive and biopsychological assessments and interpret their data: [name] ([name]) and [name] ([name])
- Hematologists/oncologists to refer participants to the project, record biomarkers, and medically interpret the results: [name] ([name]), [name] ([name]), [name] ([name]), [name] ([name]), and [name] ([name]).
- Teaching and research staff: [name] ([name]), expert in psychotherapeutic interventions; [name] ([name]), national reference for pain in children and adolescents and telemedicine; and [name] ([name]), expert in health technologies.
- Formal collaboration of a representative of the Spanish Association Against Cancer (citizen participation): [name] ([name]), to identify unmet needs during the care process.
- Additional citizen participation (non-formal collaborators) from ASION: [name] ([name]) and [name] ([name]); to identify unmet needs during the care process.

PROJECT DEVELOPMENT STAGES

- November-December 2025** (experimental group) and **July-August 2026** (recycled waiting list): Pre-intervention neurocognitive, biopsychological (conducted by psychologists), and connectome (conducted by an external company) assessment.
- March 2026-July 2026** (experimental group) and **September 2026-February 2027** (recycled waiting list): Cognitive training and mindfulness.
- July-August 2026** (experimental group) and **March-April 2027** (recycled waiting list): Post-intervention neurocognitive, biopsychological, and connectome assessment.
- December 2026** (experimental group) and **August 2027** (recycled waiting list): Biopsychological assessment at 6 months follow-up.

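### The 2x3 ANCOVA has no 6-month data for any primary performance test, and no outcome has an untreated control at 6 months

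*Protocol*

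**What the plan says.** Methods item 5 (Statistical analyses) describes one set of analyses jointly for both objectives. The lead model is a mixed 2x3 ANCOVA with an "intergroup factor, with two levels: experimental group versus control" and a "repeated measures factor, with three levels: pre-intervention, post-intervention, and six months". No outcome is excluded from it. The same item adds "In turn, latent growth curve models will be developed", naming neither outcomes nor occasions, and later states that "multiple regression analyses will be performed to predict post-treatment and 6-month follow-up measures (neurocognitive and biopsychological").

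Methods item 3 (Outcome variables) sets the visit content. "In pre-/post-intervention phases, primary variables will be measured using performance tests": SDMT, CPT-3, ECM, VFT and STROOP. The secondary questionnaires, CAMM, biomarkers and EEG connectome are also placed at pre and post. The interim visit, three months in, consists of BASC-3 alone. For the last visit the schedule lists five instruments and no performance test: "at the 6-month follow-up after the end of both interventions, the BRIEF-2, BASC-3, BPI, AIQ, and PROMIS questionnaires will be included".

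The project development stages agree with item 3. The post visit covers neurocognitive, biopsychological and connectome assessment; the 6-month visit is biopsychological only, in December 2026 for the experimental group and August 2027 for the waiting list. Treatment is dated "March 2026-July 2026 (experimental group) and September 2026-February 2027 (recycled waiting list): Cognitive training and mindfulness". Methods item 4 (Procedure) confirms that the waiting list starts the interventions once the first group has finished its 24 sessions.

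**The concern.** The statistical section asks for data that the visit schedule does not collect. The third level of the repeated factor is empty by design for every primary outcome, so the first-named efficacy analysis cannot be carried out for the variables on which the trial is to be judged.

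A second problem affects the outcomes that do reach 6 months. The model labels its groups experimental and control at all three times, but by the last one the control group has moved to treatment. A group-by-time interaction would then pool a contrast with a possible untreated control (post) and one without (6 months). Similar group means at 6 months could reflect treatment of the waiting list rather than a fading effect, and the model cannot tell these apart.

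**Working it through.** The protocol gives no power, effect-size or variance figure that bears on this point, so there is no stated number to reproduce. The check crosses the schedule with the planned analyses.

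**Step 1. Occasions per measure** (Methods item 3, project development stages)

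| Measure | Pre | 3 months | Post | 6 months | Occasions |
|---|---|---|---|---|---|
| SDMT, CPT-3, ECM, VFT, STROOP (primary) | yes | no | yes | no | 2 |
| CAMM, EEG connectome, biomarkers | yes | no | yes | no | 2 |
| BRIEF-2, BPI, AIQ, PROMIS | yes | no | yes | yes | 3 |
| BASC-3 | yes | yes | yes | yes | 4 |

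Total: 5 + 3 + 4 + 1 = 13 measures. With a 6-month value: 4 + 1 = 5, all secondary. Without: 5 + 3 = 8. Primary tests with a 6-month value: 0 of 5. For the 8 measures the design is at most 2x2.

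**Step 2. Growth curves.** With T occasions there are T means and T(T+1)/2 variances and covariances. A linear latent growth model has 2 latent means, 2 latent variances and 1 covariance (5 parameters), plus 1 residual variance if equal or T if free.

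- T = 2: 2 + 3 = 5 moments against 6 or 7 parameters; df = -1 or -2. Not identified.
- T = 3: 3 + 6 = 9 moments against 6 or 8 parameters; df = 3 or 1. Identified.
- T = 4: 4 + 10 = 14 moments against 6 or 9 parameters; df = 8 or 5. Identified.

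So the 8 pre/post-only measures cannot carry the standard model, while BRIEF-2, BPI, AIQ, PROMIS and BASC-3 can.

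**Step 3. Regressions.** Post-treatment regressions of both kinds have data. At 6 months the five questionnaires have data and the performance tests have none.

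**Step 4. The comparator at 6 months.** There are two ways to align the groups.

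- By time since own treatment: the waiting list's 6-month visit is August 2027, after its full course (September 2026 to February 2027). Treated is compared with treated.
- By calendar: the experimental visit is December 2026. No waiting-list visit is scheduled then, and that group would already be in treatment for between 62 days (30 September to 1 December, 62/7 = 8.9 weeks) and 121 days (1 September to 31 December, 121/7 = 17.3 weeks).

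Neither alignment gives an untreated observation, for any outcome.

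**Step 5. The control's pre and post.** The only waiting-list assessment dated before its own treatment is July-August 2026, the same window as the experimental group's post visit. The experimental baseline is November-December 2025, and no waiting-list assessment is scheduled then. If July-August 2026 is the control post value, the control pre value has no stated source. Patients come from Study 1, so Study 1 scores might serve, but that is an assumption; the protocol does not say so.

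**The case against.** The best defence is that the defect is narrower than it may look. A reader might infer that the growth curves and 6-month regressions cannot be run at all. The documents do not support that: item 5 ties the growth curves to no outcome, and five questionnaires have three or four occasions. The 6-month questionnaire regressions have data and need no untreated control. Parent-rated BRIEF-2 measures executive function and could arguably count as neurocognitive at 6 months. A reader might also infer that BASC-3, with its extra occasion, is the only growth-curve candidate; the count for three occasions shows otherwise. Nor does the schedule imply that waiting-list children are assessed in mid-treatment in December 2026, since they have no visit then. All of this stands.

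Two further points stand in part. Biomarkers come from routine control tests, so a later value may exist in the records, although none is scheduled. With residual variances fixed, a two-occasion growth model is just identified (5 moments, 5 parameters), but it then only describes change from pre to post.

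A statistical analysis plan might restrict the model by outcome. It could not supply performance tests that were never given at 6 months, nor an untreated group after crossover. The core is therefore unaffected.

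**Conclusion.** The point holds in this form. The 2x3 ANCOVA cannot be fitted to any of the five primary performance tests, nor to CAMM, EEG connectome or biomarkers on the scheduled assessments: 8 of 13 measures. For the same measures a standard linear growth curve is not identified, and the 6-month regressions have no performance-test outcome to predict. For the five questionnaires the model can be computed, but its experimental-versus-control contrast at 6 months has no untreated comparator on either alignment of the groups.

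This rests on reading the visit content in Methods item 3 as complete, which the project development stages support, and on the work-plan dates. The growth-curve statement assumes a linear model with estimated residual variances. The protocol should be corrected before the analysis, because its lead model cannot be carried out for the primary outcomes.

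**What to change.** Reconcile Methods items 3 and 5 with the project development stages, as follows.

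1. For the performance tests, CAMM, EEG connectome and biomarkers, replace the 2x3 model with a controlled pre/post comparison: post score, experimental versus waiting list, adjusted for baseline.
2. State which waiting-list measurements are the control pre and post. If July-August 2026 is the control post, name the source and date of the control baseline. Without one, the baseline-adjusted comparison cannot be run either.
3. Limit three-occasion models and growth curves to BRIEF-2, BPI, AIQ and PROMIS (three occasions) and BASC-3 (four).
4. Restrict 6-month inference to within-group maintenance from post to 6 months and to AB versus BA, where both sequences have been treated. Make no experimental-versus-control claim at 6 months.
5. Limit the 6-month regressions to the questionnaire measures, and say whether BRIEF-2 is classed as neurocognitive.

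Items 1, 3, 4 and 5 are wording changes and use data already scheduled. Item 2 may cost more: if no usable earlier measurement exists, a control baseline assessment is missing from the schedule. Adding performance tests at 6 months would fill the empty level but would not restore an untreated comparator. The scientific cost is the loss of a controlled 6-month efficacy claim, which the waiting-list design cannot support.

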4. Procedure: Participants will be randomized into two subgroups, which will be equally randomized into one of the following two intervention implementation sequences, according to an intragroup Latin square equal weighting technique (AB/BA design). (Fontes-de-Gracia et al., 2020): 1st sequence) Cognitive training (weeks 1-12) + Mindfulness-based emotional regulation (weeks 13-24); 2nd sequence) Mindfulness-based emotional regulation (weeks 1-12) + Cognitive training (weeks 13-24). This equal weighting technique will allow for systematic control of progressive error (order or period), without the need for a washout period between the two interventions, due to a potential residual or carry-over effect, as the treatments do not interfere with each other and are of a different nature (neurocognitive intervention versus emotional intervention).

Each intervention will last 12 weekly sessions, with a total sequence of 24 weeks for both treatments. The group of participants on the waiting list (control group) will remain there until after the 24 sessions, at which point they will begin the same process described above for randomization into subgroups and sequences for implementation of the interventions. Each treatment sequence will have a total of 10 participants assigned to it, in two age-differentiated groups (8-12 versus 13-18 years old), with 5 participants per group. Given this small sample size per group, in order to facilitate smooth interaction among participants, one of the pre-intervention scores (Emotional Regulation Index, BRIEF-2) will be used as a blocking variable, in addition to age, artificially dichotomized according to a cutoff point (resulting in low and high values on that index), thus maximizing the control of extraneous intergroup variables. Consequently, four subgroups of patients will be created by combining the levels of two blocking variables: age (8-12 versus 13-18 years) and Emotional Regulation Index score (low versus high values).

Subsequently, after assigning an anonymized code to each patient, using web-based randomization software, each treatment administration sequence (AB/BA) will be randomly assigned to each of the four patient subgroups.

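### For the five secondary questionnaires repeated at six months, the mixed 2x3 ANCOVA by default discards a child's pre and post scores when only the 6-month form is missing

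*Protocol*

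**What the plan says.** The main longitudinal analysis is given in the protocol, METHODS, 5. Statistical analyses: "First, mixed 2x3 ANCOVAs will be used", with experimental versus control as the between-group factor and a "repeated measures factor, with three levels: pre-intervention, post-intervention, and six months". The covariate is time since the last medical treatment. The follow-up procedures are those of the classical method: pairwise contrasts chosen by whether sphericity holds, omega squared as the overall effect size, and a rank-based analogue (with Kendall's W for the repeated factor) if assumptions fail. One further sentence reads "In turn, latent growth curve models will be developed"; it gives no estimator, role or priority.

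METHODS, 3. Outcome variables fixes what is measured when. For the main outcomes: "In pre-/post-intervention phases, primary variables will be measured using performance tests". For the last visit: "at the 6-month follow-up after the end of both interventions, the BRIEF-2, BASC-3, BPI, AIQ, and PROMIS questionnaires will be included". CAMM, the biomarkers and the EEG are also pre and post only.

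On losses, METHODS, 6. Limitations, biases, and contingency plan says "given that participant loss is expected in any clinical trial" and answers by recruiting more participants from the preceding study. It gives no expected rate. The document states no rule for incomplete data.

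**The concern.** A classical repeated-measures ANCOVA needs one complete row per child. A child who finishes both interventions and completes the pre and post questionnaires, but not the 6-month form, has an incomplete row and by default leaves the whole analysis of that questionnaire. The end-of-treatment comparison, for which this child has full data, then depends on a form due six months later. The rank-based fallback does not avoid this, because Kendall's W also needs complete blocks. Recruiting a replacement does not bring the discarded scores back.

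At stake is precision in a trial with 20 children per arm, on five secondary outcomes. There is also a possible bias if the children who miss the last form differ in outcome from those who return it, and differ in a way that is not the same in the two arms.

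**Working it through.** **Inputs from the protocol.** Sample size (METHODS, 2. Participants): 20 treated first and 20 on the waiting list. The head count agrees with METHODS, 4. Procedure: 2 sequences x 2 age groups x 5 = 20, and 20 + 20 = 40. It cannot be reproduced as a power calculation, because no effect size, SD, alpha or dropout rate is given.

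**Assumptions, not in the documents.** Share m of children missing only the 6-month form: 10, 20 or 30%, equal in both arms. Pre-post correlation rho = 0.6 (range 0.4 to 0.8). Two-sided alpha 0.05. Effects in baseline SD units. Both arms have a pre and a post value at matching times.

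**Step 1: children left.** 40 x (1 - m) = 36, 32, 28, that is 18, 16, 14 per arm.

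**Step 2: standard error of the pre-to-post contrast.** SD of change = sqrt(2(1 - rho)) = sqrt(0.8) = 0.894. SE = 0.894 x sqrt(2/n), with n per arm. The ratio to the full-data SE is 1/sqrt(1 - m), whatever rho is.

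| m | n per arm | SE (SD units) | ratio to n = 20 |
|---|---|---|---|
| 0 | 20 | 0.283 | 1.000 |
| 10% | 18 | 0.298 | 1.054 |
| 20% | 16 | 0.316 | 1.118 |
| 30% | 14 | 0.338 | 1.195 |

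**Step 3: power under the normal approximation.** For a 0.8 SD effect at rho 0.6, power is 0.807 with all pre/post data and 0.765, 0.716, 0.658 with complete cases. For 0.5 SD it is 0.424 against 0.389, 0.352, 0.315. At 20% missing and 0.8 SD, it falls from 0.637 to 0.542 at rho 0.4 and from 0.979 to 0.947 at rho 0.8.

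**Step 4: bias.** Simulation of 20,000 trials of 20 versus 20, with correlations pre-post 0.60, pre-6 months 0.55 and post-6 months 0.65, and a true effect of 0.50 SD. Where missingness depends on outcome, its log-odds change by 1 per SD of the post score, measured from the child's own arm mean. Mean estimates from complete triples:

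| Who misses the 6-month form | 10% | 20% | 30% |
|---|---|---|---|
| Poor post scores, treated arm only | 0.54 | 0.57 | 0.60 |
| Poor post scores, both arms alike | 0.50 | 0.50 | 0.50 |
| Good post scores, treated arm only | 0.47 | 0.43 | 0.40 |

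Using all pre/post pairs gives 0.50 throughout. The simulation compares complete triples with all pairs; it does not fit the mixed model itself.

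**Step 5: which outcomes.** Five questionnaires have a 6-month value, and all are secondary. The primary performance tests have none, so the 2x3 model cannot be fitted to them for any child; that is a mismatch between METHODS 3 and METHODS 5, not a dropout problem.

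**Step 6: the 6-month column for controls.** The waiting list starts the interventions after the 24 sessions (METHODS, 4. Procedure). In PROJECT DEVELOPMENT STAGES its only 6-month assessment is August 2027, after its own treatment, while the experimental group's is December 2026. No untreated control value exists at six months.

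**The case against.** The protocol never says that incomplete cases are removed. An ANCOVA can follow multiple imputation, and missing-data rules are commonly left to a statistical analysis plan, which is not at hand. This stands as a limit: deletion is the default of the named method, not a stated rule. It does not remove the point, because the protocol does fix the model, and that model makes a valid pre/post comparison hang on a later form.

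The same section also plans latent growth curve models, which are usually fitted by full-information likelihood and can keep incomplete cases, and it plans pairwise tests, which could use available pairs. This stands in part. A remedy may lie within the plan, but neither the estimator, nor the ranking against the ANCOVA, nor the use of available pairs is fixed.

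A reader might infer that any missed visit removes a child from every outcome. The documents do not support that. The intermediate BASC-3 is not a level of the repeated factor, so missing it drops nobody, and no primary outcome can lose data through the 6-month form.

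A reader might also infer that the treatment effect will be overstated. That needs poor responders to be lost in the treated arm only. The same mechanism in both arms gives no bias, and the reverse in the treated arm gives understatement. Nothing in the protocol favours one of these.

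Last, a mixed model does not create an untreated control at six months. This stands, and it shapes the fix.

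**Conclusion.** The point holds for BRIEF-2, BASC-3, BPI, AIQ and PROMIS. With the model as named, the default analysis leaves 36, 32 or 28 of 40 children at an assumed 10, 20 or 30% missing, and the standard error of the end-of-treatment contrast rises by about 5, 12 or 20%. This precision loss follows from the head count alone once a missing rate is assumed. It also takes for granted that rows in the two arms are otherwise complete, which the waiting list's schedule makes uncertain for the 6-month column. The power figures rest in addition on the assumed correlation, effect and alpha.

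Bias is possible in either direction if missingness depends on outcome differently by arm, but no direction can be claimed. The matter concerns secondary outcomes only. It is still worth correcting, because the loss is of data already collected, in a small trial, and can be avoided.

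**What to change.** For the five questionnaires, name a linear mixed model as the main analysis: REML, visit as a categorical factor, unstructured covariance, Kenward-Roger degrees of freedom, group-by-visit terms where both groups are comparable, the same covariate, and every available occasion of every randomised child. State that it is valid if data are missing at random. State the role of the growth curve models relative to it.

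Take the experimental-versus-waiting-list effect from the end-of-treatment contrast only, and report six months as within-group follow-up. Analyse the primary performance tests with a pre/post model.

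The contrast also needs waiting-list scores at the start and end of the waiting period. PROJECT DEVELOPMENT STAGES dates only one waiting-list assessment before its treatment (July-August 2026), so the amended text should say which scores serve as its pre and post values.

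The model change costs a rewritten paragraph and a different procedure in standard software, with no new patients or visits.

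### If normality fails, the only non-parametric methods the protocol names are one-factor tools that carry neither the covariate nor the group-by-time contrast of Hypothesis 1

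*Protocol*

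**What the plan says.** All of this is in the Protocol, METHODS, item 5 (Statistical analyses).

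- **Main model:** "mixed 2x3 ANCOVAs will be used (intergroup factor, with two levels: experimental group versus control", crossed with a "repeated measures factor, with three levels: pre-intervention, post-intervention, and six months". The model is adjusted by "controlling for confounding variables (time elapsed since completion of the last treatment received: chemotherapy, TPH, or CAR-T".
- **Fallback for the main model:** "in the event of non-compliance with statistical assumptions such as normality, non-parametric analog models will be used". No such model is named.
- **Fallback between groups:** "in the event of non-compliance with parametric assumptions such as normality, the Mann-Whitney U test will be used for pairwise comparisons", with a Bonferroni correction. This replaces Tukey HSD and Games-Howell.
- **Fallback within groups:** "non-parametric pairwise comparisons will be performed using the Wilcoxon test together with a Dunn-Sidak post hoc correction". This replaces Tukey WSD and Roy-Bose.
- **Non-parametric effect sizes:** Freeman's Theta and Cliff's Delta for the between-group factor; Kendall's W and a rank biserial correlation for the within-group factor.
- **Interaction:** "for the interactive term, the effect size index f will be chosen as an omnibus test", with Cohen's d for simple effects. No non-parametric counterpart is given.

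Latent growth curve models are planned as well, but not as the fallback. Hypothesis 1 concerns changes after treatment relative to the waiting list.

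**The concern.** Hypothesis 1 is about a difference between arms in change, which is the group-by-time term. The parametric route tests it and adjusts for time since treatment. On the non-parametric route the protocol goes into detail for each factor (test, multiplicity correction, omnibus and pairwise effect size) but names nothing for the interaction and no way to carry the covariate.

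An analyst following the named methods would report an unadjusted between-arm comparison and separate within-arm comparisons. Two outcomes in the same trial could then be judged on different questions, depending only on whether each met a distributional assumption. With 40 patients and several primary performance tests, that would make the results hard to read together and could cost power.

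**Working it through.** **1. What each named tool can do.**

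| Tool | Factor covered | Takes a covariate | Tests group by time |
|---|---|---|---|
| Mann-Whitney U, Cliff's Delta | group | no | no, unless applied to change scores (not stated) |
| Freeman's Theta | group | no | no |
| Wilcoxon, rank biserial | time | no | no |
| Kendall's W | time | no | no |
| f, Cohen's d | interaction, simple effects | parametric route only | parametric route only |

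The between-group factor has two levels. There is only one pair to compare, so the pairwise Mann-Whitney is the between-group test and not a follow-up to a wider one.

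**2. What this could cost.** The protocol states no alpha, effect size, SD or correlation, so there is no figure of its own to reproduce. Inputs:

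- 20 per arm (METHODS, item 2).
- Assumed: two-sided alpha 0.05, true effect 0.7 SD, pre-post correlation r of 0.3 to 0.8.
- The time-since-treatment covariate is left out of the illustration.

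METHODS, item 3 lists the primary performance tests before and after intervention only. For these the group-by-time term reduces to comparing pre-post change between arms. The effect in units of the relevant SD is:

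- post score alone: 0.7 / 1 = 0.70 at any r;
- change score: 0.7 / √(2(1 − r)), which is 0.59, 0.70, 0.90 and 1.11 at r = 0.3, 0.5, 0.7 and 0.8;
- post score adjusted for pre score: 0.7 / √(1 − r²), which is 0.73, 0.81, 0.98 and 1.17.

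Power by simulation with normal scores, 4,000 to 5,000 trials per setting; ranges show the spread between separate runs:

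| r | Mann-Whitney, post | Mann-Whitney, change | t-test on change (planned contrast, two times) | Rank ANCOVA on pre score |
|---|---|---|---|---|
| 0.3 | 54-58% | 42% | 44% | 58-59% |
| 0.5 | 54-58% | 54-57% | 59% | 65-70% |
| 0.7 | 54-58% | 77-78% | 79% | 80-82% |
| 0.8 | 54-58% | 91% | 93% | 90-91% |

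Type I error was about 5% throughout (4.4% to 5.8%). Mann-Whitney on post scores and rank ANCOVA use ranks only, so log-normal scores give the same picture (about 56% against 80% at r = 0.7).

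**3. Reading the table.** Against rank ANCOVA, Mann-Whitney on post scores is lower at every correlation: little at 0.3, about 25 points at 0.7. Against the planned change contrast, it is well below at 0.7 and above, close at 0.5, and ahead at 0.3. Mann-Whitney on change scores recovers most of the loss at 0.7 or more and none at 0.5, and it still omits the covariate.

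**The case against.** The strongest reply is that Mann-Whitney and Wilcoxon are named for pairwise comparisons only. The sentence on the main model sends it to non-parametric counterparts, and such a counterpart of a mixed design can keep the interaction and sometimes a covariate. The exact method could properly sit in a statistical analysis plan that is not shown. The study also calls itself a pilot phase and makes no power claim.

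Much of this stands, and it rules out several stronger readings that a reader might infer:

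- **That the protocol drops the interaction test.** It does not say so. It leaves the replacement model open.
- **That baseline is discarded.** In the planned model the pre-intervention score is a level of the time factor, not a covariate. Wilcoxon pairs can include it, and Mann-Whitney on change scores is not excluded.
- **That the switch will be triggered often by routine checks.** No normality test, threshold or unit of checking is stated, so no trigger rate can be derived.
- **That within-arm Wilcoxon tests are a special hazard.** A practice effect can make any within-arm contrast significant, including a paired t-test. This is not peculiar to the fallback.

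What the reply does not meet is the pattern of what is named. The protocol gives even its omnibus non-parametric effect sizes factor by factor and leaves the interaction with parametric indices only. An analysis plan built on this text would inherit that gap.

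**Conclusion.** The point holds as a gap in what the fallback route names. That route has no identified test of group by time and no identified way to adjust for time since treatment, while the tests it does name answer a one-factor, unadjusted question. It is not a threat to type I error, since all methods compared hold about 5%.

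The likely harm is inconsistency between outcomes and, if post scores are compared, lost power: roughly 55% against 80-82% for rank ANCOVA at an assumed 0.7 SD and correlation 0.7. The size depends on the correlation, which the protocol does not give, and on whether raw or change scores are used, which it does not state. The power figures show direction only. The wording should be corrected before analysis.

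**What to change.** Name the fallback for the main model, and choose one that keeps both the arm contrast in change and the covariate. Either of these would serve:

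- at each post-baseline time compared between arms, a rank ANCOVA of the outcome on arm, pre-intervention score and time since last treatment; or
- a permutation test of the arm or group-by-time coefficient in the planned model, which stays closest to the planned contrast.

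State that normality is judged on model residuals. Report Mann-Whitney, Wilcoxon and their effect sizes as descriptive follow-up only, and give an interaction effect size that matches the chosen fallback.

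The cost is a few sentences of analysis text, with no change to conduct or data collection. A rank-scale effect is harder to read clinically, and rank ANCOVA loses a few points of power if the data are in fact normal (about 84% to 80% at correlation 0.7, against ordinary ANCOVA on the pre score). Rank ANCOVA also moves the pre-intervention score from a time level to a covariate, which should be said openly.
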